#### 9.4.8. Proportion of Responders Achieving and Maintaining a sUA Below 5 mg/dL

The proportion of responders is defined as subjects achieving and maintaining sUA < 5 mg/dL for at least 80% of the time during Month 3, Month 6, Month 9, and Month 12. These will be calculated and analyzed using the same method described for the primary efficacy endpoint ([Section 9.2](#)), secondary endpoint reported in [Section 9.3.1](#), and exploratory endpoints reported in [Sections 9.4.5 and 9.4.6](#).

#### 9.4.9. Change from Baseline in sUA

Observed values and change from baseline at each scheduled time point, including pre-infusion and post-infusion results for sUA will be summarized using descriptive statistics (i.e. n, mean, standard deviation, median, 25th quartile, 75th quartile, minimum, and maximum). Changes from baseline for pre-infusion sUA (or available sUA at visits with no infusion, e.g., Weeks 21 and 23) to each visit and overall will be analyzed with an MMRM ANCOVA model as described in [Section 9.4](#).

Line plots of the observed mean pre-infusion sUA values with 95% CI at each scheduled visit will be presented using the ITT population by pegloticase treatment status (On Treatment and Overall) and treatment group. A graphical presentation of the mean pre-infusion sUA values by treatment group and Month 6 sUA responders vs. non-responders, based on the primary endpoint definition of Month 6 response, will also be produced for the ITT population.

#### 9.4.10. Time to First sUA > 6 mg/dL Following the First Infusion

The first pegloticase infusion date will be the reference date (REFDATE). Only the scheduled pre-infusion sUA values starting with Week 2 will be considered for determination of the endpoint. As was noted in [Section 9.1](#), the local laboratory's value may be used if the central laboratory's value at the scheduled time point is unavailable. The days until the sUA > 6 mg/dL will be calculated as:

EVT DAYS = (EVNTDATE – REFDATE) + 1, where EVNTDATE is the date of the earliest post-reference date where the pre-infusion sUA value (from central lab, or local if central is unavailable) is > 6 mg/dL. For subjects who do not have any sUA values > 6 mg/dL, their EVNTDATE will be censored at the latest collected sample with non-missing sUA result through Week 52. Kaplan-Meier (KM) estimates will be provided by treatment group of the 25th percentile, median, and 75th percentile. 95% CIs of the median will be provided for the median. Further, a log-rank test stratified by presence of tophi (yes, no) will be provided.

Plots of the time to first sUA > 6 mg/dL will be provided by treatment group using KM curves.

This document is confidential.

#### 9.4.11. Time to Two consecutive sUAs > 6 mg/dL Following the First Infusion

The first pegloticase infusion date will be the reference date (REFDATE). Only the scheduled pre-infusion sUA values from the central laboratory starting with Week 2 will be considered for determination of the endpoint. As was noted in Section 9.1, the local laboratory's value may be used if the central laboratory's value is unavailable. The days until the sUA > 6 mg/dL will be calculated as:

EVT DAYS = (EVNTDATE – REFDATE) + 1, where EVNTDATE is the date of the first of the two consecutive post-reference dates where the pre-infusion sUA value (from central lab, or local if central is unavailable) was > 6 mg/dL. For subjects who did not have two consecutive sUA values > 6 mg/dL, their EVNTDATE will be censored at the latest collected sample with non-missing sUA result through Week 52. Subjects with only a single elevated pre-infusion sUA and no subsequent sUA results available will be considered to have the event. Kaplan-Meier estimates will be provided by treatment group of the 25th percentile, median, and 75th percentile. 95% CIs of the median will be provided. Further, a log-rank test stratified by presence of tophi (yes, no) will be provided.

Plots of the time to two consecutive sUA > 6 mg/dL will be provided by treatment group using KM curve.

#### 9.4.12. Percentage of Non-Hyperuricemic (sUA < 6 mg/dL) Time during Months 3, 6, 9 and 12

The proportion or percentage of time  $P = 100 * \frac{W_1}{T_1}$  of non-hyperuricemic (sUA < 6 mg.dL) during Months 3, 6, 9, and 12 are defined in Section 9.4.5, Section 9.2, Section 9.3.1, and Section 9.3.2.

The proportion or percentage of time during the month where the sUA was less than 6 mg/dL will be summarized using descriptive statistics (i.e. n, mean, standard deviation, median, minimum, and maximum). The proportion or percentage of hours will be analyzed with an MMRM ANCOVA model as described in Section 9.4.

#### 9.4.13. Change from Baseline in HAQ-DI, HAQ Pain, and HAQ Health to Weeks 24 and 36

The analysis of the change from baseline in HAQ scores to Weeks 24 and 36 are described in Section 9.3.3.

[figure not shown]

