### **9.2. Primary Efficacy Endpoint and Analysis**

This study will compare pegloticase 8 mg co-administered with MTX to pegloticase 8 mg co-administered with placebo in subjects with uncontrolled gout. The primary efficacy endpoint is the proportion of Month 6 (Weeks 20, 21, 22, 23, and 24) responders, defined as subjects achieving and maintaining sUA < 6 mg/dL for at least 80% of the time during Month 6. The objective is to demonstrate superiority of pegloticase given with MTX over pegloticase given with placebo. The primary comparison will be made for ITT population, i.e., all randomized subjects, regardless of adherence to study treatment. The comparison is between randomized (planned) treatment groups of pegloticase given with MTX over pegloticase given with placebo.

[figure not shown]

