### **9.3. Secondary Efficacy Endpoints and Analyses**

#### **9.3.1. Proportion of Month 12 Responders**

The proportion of Month 12 (Weeks 48, 50, and 52) responders, will be defined as subjects achieving and maintaining sUA < 6 mg/dL for at least 80% of the time during Month 12.

This endpoint will be analyzed for the ITT and mITT populations.

This determination will be completed using the same linear interpolation method described for the primary efficacy endpoint in Section 9.2.1. The Month 12 period will include pre-infusion and post-infusion results at Week 48, pre-infusion and post-infusion results at Week 50, pre-infusion results at Week 52, and unscheduled assessments of sUA collected between Week 48 and Week 52 processed by the central laboratory. Section 9.1 shows the rules for inclusion of sUA values reported by local laboratories.

If the subject's proportion of hours where sUA was less than 6 mg/dL, P, is greater than or equal to 80% the subject will be called a responder for the Month 12 responder endpoint. Subjects meeting the stopping rule, i.e. has pre-infusion sUA values greater than 6 mg/dL at 2 consecutive scheduled visits (starting at Week 2) through Week 52 will be counted as non-responders. A subject with the proportion of hours, P, less than 80% will be counted as non-responders.

There will be no imputation of sUA values due to missing values among those collected between Week 48 and Week 52, unless missing data is due to "Site Closure". At least two sUA observations from different visits must be available in order for a subject to be eligible for consideration as a responder. Subjects with only one sUA observation will be considered a non-responder, regardless of the value of that single observation. For subjects with "Site Closure" missing data (as defined in Section 6.3.3) during Month 12, the rules described in Section 6.3.3 will be applied. The proportion of Month 12 responders will be analyzed using the same multiple imputation method and the stratified weighting approach specified for primary analysis of the primary endpoint.

In addition, the proportion of responders along with a 95% confidence interval for the proportion will be summarized based on the observed data (i.e. with no imputation based on COVID-19 impact), with non-responder imputation used for subjects who meet the stopping rule or have missing results during Month 12 (this will be the primary analysis method if there are no "Site Closure subjects").

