The proportion of hours during the period where the sUA was less than 6 mg/dL (based on observed sUA) will be summarized using descriptive statistics (i.e. n, mean, standard deviation, median, 25th quartile, 75th quartile, minimum, and maximum). The number and proportion of subjects that discontinued treatment due to the stopping rule will be summarized. The number and proportion of responders will be summarized along with a 95% exact (Clopper-Pearson) CI for the proportion. In addition, the number and proportion of subjects with data available at Week 52 responder, data available at Week 52 non-responder (subcategories of met stopping rule at or before Week 52, did not meet stopping rule), and data not available at Week 52 non-responder (subcategories of met stopping rule at or before Week 52, missing data for other reason) will be summarized.

The proportion of sUA < 6 mg/dL responders during Month 12 will be plotted.

The subgroup analyses for proportion of Month 12 responders will be performed using an unstratified chi-square test within each subgroup category (Section 6.6) for the ITT population using same method as for the subgroup analysis of the primary endpoint. If there are at least 20 subjects in a subgroup category, a difference in response rates with a two-sided 95% CI, calculating using normal theory, will be reported.

#### 9.3.2. Proportion of Subjects Having Tophi at Baseline with Complete Resolution of $\geq 1$ Tophi at Week 52

Digital photography will be used to assess tophi. Digital photography of the hands and feet will be completed at Week -6, Day 1 and Weeks 14, 24, 36, and the End of Pegloticase Infusions Visit (if applicable) and Week 52/End of Study/Early Termination and the 3 and 6 month Post Treatment Follow-up Visits. Other anatomical sites with large tophi may be photographed in addition to the hands and feet at the Investigator's discretion.

All measurable tophi will be measured bi-dimensionally (using the longest diameter and the longest perpendicular to that diameter) and the response of each individual tophus will be categorized according to the change from baseline in area of each tophus at each visit as follows:

- Complete Response (CR) – A 100% decrease in the area of the tophus
- Marked Response (MR) – At least a 75% decrease in the area of the tophus
- Partial Response (PR) – At least a 50% decrease in the area of the tophus

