#### **9.4. Exploratory Efficacy Endpoints and Analyses**

All exploratory analyses will be performed on the ITT Population unless otherwise specified. For the exploratory efficacy endpoint analysis of continuous variables, a mixed model repeated measures (MMRM) analysis of covariance (ANCOVA) model will be fit to the individual change from baseline value for the parameter of interest, with terms for baseline score, tophi presence at baseline, and factors of treatment group, visit, visit by treatment group interaction and visit by baseline interaction. The Post Treatment Follow-up Month 3 and Month 6 visits will not be included in the MMRM model. The unstructured (UN) variance-covariance matrix will be used. In the event that this matrix does not allow for model convergence, the following three variance-covariance matrices will be attempted in order until one converges: heterogeneous Toeplitz (TOEPH), heterogeneous compound symmetry (CSH), and Toeplitz (TOEP). The p-values for all terms in the model will be presented, as well as the treatment group LS means and associated SE, and their difference, SE of the difference, 95% CIs and p-value, overall and at each visit.

P-values for exploratory endpoints will be provided for descriptive purposes only.

No imputation of missing data will be performed for the exploratory analysis of continuous variables, as the analysis will be performed using MMRM models, which accommodate missing data and allow information from every visit to contribute to the analysis of the data. The only exception to this is that for any subject in the ITT Population without post-baseline values (unless “Site Closure”), a change from Baseline value of 0 will be imputed at the first post-baseline visit (in order to avoid exclusion from the MMRM analysis). Subjects with no post-

baseline assessments due to site closure will be excluded from analysis. Otherwise, all available data for subjects impacted by COVID-19 will be included.

For exploratory efficacy endpoint analysis of categorical variables, either CMH or chi-square test (for endpoints related to tophi) will be used.

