#### 9.4.5. Proportion of Month 9 Responders

The proportion of Month 9 (Weeks 32, 34, and 36) responders, will be defined as subjects achieving and maintaining sUA < 6 mg/dL for at least 80% of the time during Month 9.

This endpoint will be analyzed for the ITT population.

This determination will be completed using the same linear interpolation method described for the primary efficacy endpoint in Section 9.2.1. The Month 9 period will include pre-infusion and post-infusion results at Week 32, pre-infusion and post-infusion results at Week 34, pre-infusion results at Week 36, and unscheduled assessments of sUA collected between Week 32 and Week 36 processed by the central laboratory. Section 9.1 shows the rules for inclusion of sUA values reported by local laboratories.

If the subject's proportion of hours where sUA was less than 6 mg/dL, P, is greater than or equal to 80% the subject will be called a responder for the Month 9 responder endpoint. Subjects meeting the stopping rule, i.e. has pre-infusion sUA values greater than 6 mg/dL at 2 consecutive scheduled visits (starting at Week 2) through Week 36 will be counted as non-responders. Subjects with the proportion of hours, P, less than 80% will be counted as non-responders.

There will be no imputation of sUA values due to missing values among those collected between Week 32 and Week 36, unless missing data is due to site closure. At least two sUA observations from different visits must be available in order for a subject to be eligible for consideration as a responder. Subjects with only one sUA observation will be considered a non-responder, regardless of the value of that single observation. For subjects with "Site Closure" missing data during Month 9, the rules described in Section 6.3.3 will be applied. The proportion of Month 9 responders will be analyzed using the same multiple imputation method and the stratified weighting approach specified for primary analysis of the primary endpoint.

In addition, the proportion of responders along with a 95% confidence interval for the proportion will be summarized based on the observed data (i.e. with no imputation based on COVID-19 impact), with non-responder imputation used for subjects who meet the stopping rule or have missing results during Month 9 (this will be the primary analysis method if there are no "Site Closure subjects").

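### SAP 9.4.12: the percentage of time with sUA below 6 mg/dL has faulty month cross-references and is sent to a change-from-baseline MMRM although it has no baseline value

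*SAP*

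**What the plan says.** SAP Section 9.4.12 gives the percentage as P = 100 × W1/T1 and states that the values "during Months 3, 6, 9, and 12 are defined in Section 9.4.5, Section 9.2, Section 9.3.1, and Section 9.3.2". For the analysis it says: "The proportion or percentage of hours will be analyzed with an MMRM ANCOVA model as described in Section 9.4".

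The Section 9.4 model "will be fit to the individual change from baseline value for the parameter of interest, with terms for baseline score". Its other terms are tophi presence, treatment group, visit, visit-by-treatment and visit-by-baseline, with an unstructured covariance matrix tried first. Section 9.4 also imputes a change of 0 at the first post-baseline visit for an ITT subject with no post-baseline value, unless the reason is site closure. It describes exploratory p-values as descriptive.

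SAP Section 6.2.1 defines baseline for sUA as the last single measurement before the first MTX dose. The SAP defines no pre-treatment interval over which a percentage of time could be computed.

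**The concern.** There are two separate faults. The first is in the references: one of the cited sections has nothing to do with sUA over time, and the section that sets the Month 3 window is absent. The second is in the model: it needs a change score and a baseline score, and this endpoint has neither.

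What is at stake is prespecification. The endpoint is the continuous counterpart of the monthly responder outcomes. As the text stands, the programmer must decide whether the response is the percentage or a change, which baseline covariate to use (if any), and what to do with subjects who have no post-baseline sUA.

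**Working it through.** **Step 1: match each cited section to its content, in the listed order.**

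| Month | Section cited in 9.4.12 | What that section covers | Match | Section that defines the month |
|---|---|---|---|---|
| 3 | 9.4.5 | "Proportion of Month 9 Responders" | no | 9.4.6 |
| 6 | 9.2 | Month 6, primary endpoint | yes | 9.2.1 |
| 9 | 9.3.1 | Month 12 responders | no | 9.4.5 |
| 12 | 9.3.2 | Tophus resolution at Week 52 | no | 9.3.1 |

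Read in order, 3 of 4 are wrong. The text does not say that the two lists correspond one to one. Read as a set, Sections 9.2, 9.4.5 and 9.3.1 do cover Months 6, 9 and 12, so one reference (9.3.2) is wrong and one (9.4.6) is missing.

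The ordered reading has some support. The SAP revision history records that Month 9 response moved from secondary to exploratory in version 2.0. Suppose Month 9 had been the first secondary section. Undoing the move would make 9.3.1 Month 9 and 9.3.2 Month 12, and Month 3 would step back from 9.4.6 to 9.4.5. All four references would then be right in order. This is inference about a superseded numbering, not something the documents state.

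**Step 2: the formula's symbols.** W1 and T1 are defined only in Section 9.4.7, which 9.4.12 does not cite, and there they cover Weeks 10 to 14 only. W2 and T2 cover Weeks 20 to 24. No such quantities are named for Months 9 and 12.

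**Step 3: the model without a baseline percentage.** With four monthly time points, the Section 9.4 fixed effects have these columns:

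- intercept 1, baseline 1, tophi 1, arm 1, month 3, month-by-arm 3, month-by-baseline 3
- total: 1 + 1 + 1 + 1 + 3 + 3 + 3 = 13

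The only ready-made substitute is a common constant. Protocol Section 9.3.1 requires screening sUA of at least 7 mg/dL, so 0% is the natural choice. The design matrix was built for 135 subjects (90 and 45) at four months:

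| Baseline supplied | Columns | Rank |
|---|---|---|
| 0% for all | 13 | 9 |
| 100% for all | 13 | 9 |
| varying between subjects | 13 | 13 |

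The 13 − 9 = 4 lost columns are the baseline term and the three month-by-baseline terms. The remaining 9 are 1 intercept + 1 tophi + 1 arm + 3 month + 3 month-by-arm. Every arm-by-month contrast is therefore still estimable; what disappears is the baseline adjustment.

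**Step 4: the zero-change rule.** With a 0% baseline, a change of 0 means 0% of time below 6 mg/dL. That agrees with SAP Section 9.2.2, which counts a subject with no Month 6 sUA values as a non-responder. The rule has a sensible meaning but is not written on this endpoint's scale.

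**Step 5: a fallback elsewhere.** The list of MMRM parameters in Protocol Section 9.6.5.2 includes mean sUA but not the percentage of time, so the protocol supplies no alternative model.

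**The case against.** The strongest reply is that this is a stale cross-reference and a loosely worded model, and that a competent programmer would recover the intent.

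- **The descriptive summaries are safe.** Time below 6 mg/dL is specified for each month in SAP Sections 9.2.4 (Month 6), 9.3.1 (Month 12), 9.4.5 (Month 9) and 9.4.6 (Month 3), and Section 9.4.8 cites the correct four sections for the 5 mg/dL endpoint. This stands. A reader might infer that the endpoint cannot be produced, or that Month 3 would be computed on Weeks 32 to 36. The documents do not support either: the second would contradict the title of 9.4.5 itself.
- **The response is named.** Neighbouring sections such as 9.4.9 and 9.4.14 to 9.4.16 send changes from baseline to the model, whereas 9.4.12 sends the percentage. This also stands and suggests what was meant. It does not settle the matter, because the model it points to is still defined on a change score with baseline terms.
- **The model runs with a constant baseline.** It does, and the randomised comparison stays valid. A reader might infer that the model cannot be fitted; Step 3 shows otherwise. The loss is precision, which depends on how strongly baseline sUA predicts the percentage. The documents give no figure for that.
- **Clustering near 0% and 100%.** This is plausible, but it is an expectation without a figure in either document, so the point does not rest on it.

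The example MMRM code in SAP Section 19.4 is redacted, so how the baseline terms were programmed cannot be judged.

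**Conclusion.** The point holds as a wording fault in an exploratory analysis. Section 9.4.12 cites the tophus section and omits the Month 3 section whichever way the list is read; three of four references are wrong only on the ordered reading, which is likely but not stated. The Section 9.4 model does not fit an endpoint with no baseline value. With a constant 0% baseline, 4 of 13 columns drop out, the arm-by-month contrasts survive, and no baseline adjustment remains.

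This rests on two assumptions: that the model uses the four months as its visits, and that the redacted code does not already name another covariate. No alpha is allocated to this endpoint, so no primary or secondary conclusion is affected.

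**What to change.** Amend SAP Section 9.4.12 before unblinding:

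1. Cite 9.4.6 for Month 3, 9.2.1 for Month 6, 9.4.5 for Month 9 and 9.3.1 for Month 12, and define W and T for each month's window.
2. State that the MMRM response is the percentage itself. Use pre-MTX sUA as the baseline covariate, with month-by-baseline-sUA, tophi presence, arm, month and month-by-arm. Keep the unstructured covariance already specified; with four months it has 4 × 5/2 = 10 parameters. Robust standard errors are optional.
3. Keep the imputation rule, restated on the percentage scale: a subject with no post-baseline sUA enters as 0% of time below 6 mg/dL, consistent with the non-responder rule in Section 9.2.2, and site-closure subjects remain excepted. Deleting the rule without a replacement would remove randomised subjects from an ITT analysis.

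The cost is SAP wording and the matching program code. Pre-MTX sUA is already scheduled at Screening and Week -6, so no new data are needed.

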#### 9.4.14. Change from Baseline in Tender Joint Count and Swollen Joint Count

Tender and swollen (excludes hip) joint counts will be recorded at the Week -6 (prior to the first dose of MTX); prior to pegloticase infusion at the Day 1 and Weeks 6, 14, 20, 24, 36, and 44 Visits during the Pegloticase + IMM Period; and at the End of Pegloticase Infusions Visit (if applicable) and the Week 52/End of Study/Early Termination Visit, Post Treatment Follow-up Month 3, and Post-treatment Follow-up Month 6.

Tender and swollen joint counts will be assessed using the rheumatoid arthritis 66-68 joints shown in the Figure 1 below. All information will be entered into the appropriate eCRF.

Figure 1 Rheumatoid Arthritis 66-68 Tender and Swollen Joint Counts

This document is confidential.

For tender joint count, 68 joints are assessed as tender or non-tender (1=tender, 0=non-tender), and the tender joint count is the sum of 0s and 1s over all 68 joints for each subject. For swollen joint count, 66 joints are assessed as either swollen or non-swollen (1=swollen, 0=non-swollen) and the swollen joint count is the sum over all 66 for each subject.

Observed values, change from baseline in the tender and swollen joint counts at each scheduled time point will be summarized using descriptive statistics (i.e. n, mean, standard deviation, median, minimum, and maximum). Changes from baseline for these parameters to each visit and overall will be analyzed with an MMRM ANCOVA model as described in Section 9.4.

